**Improved quality of life in children with intestinal failure
– a randomised controlled intervention trial**

Improved quality of life in children with intestinal failure.

Research questions and hypotheses, theoretical approach and methodology

We hypothesize that prebiotics will improve QoL in children with intestinal failure (IF) by reducing bacterial overgrowth and hence restore the microbiota towards a healthier gut.

Primary aim:

- Determine whether prebiotics improves QoL (primary endpoint) in IF children.

Secondary aims:

- Study changes in microbiota and production of short chain fatty acids (secondary endpoints).
- Explore effects of prebiotics on GI-symptoms, changes in tolerance for enteral nutrition and need for antibiotic treatment.

Overview

The project consists of two work packages (WPs): Effect of prebiotics on microbiota (WP1) and Effect of prebiotics on quality of life (WP2), as illustrated in figure 3. The main study (WP2) is a randomised controlled trial.

Setting: Paediatric patients with IF are routinely followed at Oslo University Hospital (OUH) by a multidisciplinary team with expertise in the treatment of IF. Patients will be identified through this team and recruited by research workers (PhD student/research assistant).

Patients: Patients aged 1 to 18 years that fit one of the inclusion criteria will be invited to participate in the study by letter.

Inclusion criteria are:

- Diagnosed with congenital malformations or diseases requiring intestinal surgery leading to short bowel syndrome.
- or
- Diagnosed with conditions and diseases leading to IF.
- and
- Treated with parenteral nutrition for a period of >3months

Exclusion criteria:

- Children in need of temporary advanced nutrition intervention due to illness, e.g. infections.
- Children with temporary malfunctioning gut due to advanced medical treatment, for example cancer treatment or transplantation

WP1. Effect of Prebiotics on microbiota (proof of concept).

The short-time effects of prebiotics on microbiota will be evaluated in an open 4-week intervention, to establish a proof of concept.

- **Task 1.1 Recruitment of participants**

The patients will be recruited in connection with routine follow-ups at OUH.

- **Task 1.2 Run-in period**

To ensure that the participants have a stable microbiota prior to the intervention we will use a run-in period before the intervention. Data collected at the start of the run-in are: QoL, Stool sample, stool consistency and use of antibiotics. Any hospital admissions or need for antibiotics during the run-in period will be recorded.

- **Task 1.3 Intervention**

Data collected before and after the intervention include: QoL, stool sample, blood samples, nutritional intake (diet, enteral and intravenous nutrition), stool consistency and use of antibiotics. Participants are provided with sachets of prebiotics to ingest daily for 4 weeks of Phase 1 intervention. The dosage will be prescribed according to weight. The patients are then invited to the hospital for a follow-up of phase 1.

WP2 Effect of Prebiotics on Quality of Health

T2.1 Randomisation of participants from Phase 1

Participants will be randomised into two groups after completing Phase 1. One group will continue to use prebiotics (Stimulance), while the other group will not receive any intervention. Microbiota is known to return to its habitual flora within few weeks after short-term intervention. The group without prebiotic treatment will therefore act as a control group.

T2.2 Intervention Phase 2

The participants in the intervention group continues with prebiotics (Stimulance) for another 6 months. The dosage will be adjusted if necessary, pending the observations in Phase 1. Data collected at the end of the intervention include: QoL, stool sample, blood samples, nutritional intake (diet, enteral and intravenous nutrition), stool consistency and use of antibiotics. We will compare the intervention group with the control group. In addition, the intervention group will serve as their own control before and after the intervention with prebiotics. The study design is useful to account for the inter-individual make-up of the microbiota that contributes to a large portion of variability between subjects.

Endpoint:

Primary endpoint will be QoL score compared between the two groups at 6-months follow-up. QoL will be scored using two published and validated questionnaires: PedsQL 4.0 and PedsQL 3.0 Gastrointestinal Symptoms Scales (PedsQL GI). Scoring will be done at run-in, before and after phase 1 and at the end of phase 2. This enables us to study changes between the two groups (primary endpoint) and changes within the subjects before and after intervention with prebiotics.

Secondary endpoint will include changes in the microbiota measured indirectly by the production of SCFAs, the microbiota composition and diversity. In addition, relevant clinical outcomes will be obtained and analysed.

Methods:

- Stool samples will be collected using a provided stool collection kit with written instructions for the participant/parents. The sample will be collected in a tube and stored at home in the freezer in a specialised container until pick-up or hospital visit. The samples will be analysed for SCFA and total organic acid content using HPLC, while microbiota will be analysed in faecal samples using established techniques (16S rRNA amplicon sequencing and reduced metagenome sequencing). Faecal inflammation biomarkers will also be analysed. The main effect of the intervention on the microbiota will be tested based on crude alpha and beta diversity indices but we will also apply advanced multivariate methods.

- Diet will be recorded before and after phase 1 and at the end of phase 2:
 - Repeated 24 hr recall (2 days). Nutritional analysis will be done by use of the software DietistPro, which is implemented and used by dieticians at OUH, as well as in the other Nordic countries (www.kostdata.se/nb/dietistnet/dietist-net-pro).
 - Questionnaire to collect data on the use of nutritional supplements, vitamin- and mineral supplements, food avoidance, food allergies, food intolerances, enteral and intravenous nutrition.
- Clinical data (blood samples, GI-function, anthropometric data and other medical information) will be collected at run-in, before and after phase 1 and at the end of phase 2.

Outcomes and measurements

Outcome	Measurements
PRIMARY	
Quality of life	QoL questionnaires: PedsQL and PedsQL Gastrointestinal symptoms scale
SECONDARY	
Faeces	SCFA (HPLC), Organic Acids (HPLC), Microbiota composition (16S rRNA amplicon sequencing and reduced metagenome sequencing), inflammation markers (calprotectin)
Blood samples:	Biomarkers of intestinal leakage (albumin, Lipopolysaccharide-binding protein, citrulline) Biomarkers of intestinal absorption (iron status, vitamin status) Infection and inflammatory parameters (CRP, ESR, full blood count)
Nutritional record	Nutrient intake from food, drink, feeding tube (enteral nutrition), intravenous nutrition and supplements
Clinical status:	Anthropometrics: Weight, height, BMI GI-Function: stool frequency and consistency (Bristol Stool Scale) Electronic patient record: Diagnosis, medical complications, antibiotic treatment

Ethical considerations:

The intervention is a limited time supplementation with prebiotics. The product (Stimulance©) is approved for enteral use and is not expected to do any harm to the participants. However, any adverse events will be recorded. The project is approved by the Regional Ethical Committee (REK), nr 170851. The project will be registered at Helsenorge.no and Clinicaltrials.gov.

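### Does the inclusion list leave open whether every child must have had more than 3 months of parenteral nutrition?

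*Protocol*

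**What the plan says.** In the protocol, the Patients paragraph opens the eligibility section with "Patients aged 1 to 18 years that fit one of the inclusion criteria will be invited to participate in the study by letter". The Inclusion criteria list then gives three items, labelled here for reference:

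- A: "Diagnosed with congenital malformations or diseases requiring intestinal surgery leading to short bowel syndrome"
- B, joined to A by *or*: "Diagnosed with conditions and diseases leading to IF"
- C, joined by *and*: "Treated with parenteral nutrition for a period of >3months"

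No bracket or sentence states the grouping. The Setting paragraph says where the children come from: "Paediatric patients with IF are routinely followed at Oslo University Hospital (OUH) by a multidisciplinary team with expertise in the treatment of IF". That same team identifies the candidates. The first exclusion criterion removes "Children in need of temporary advanced nutrition intervention due to illness, e.g. infections"; the second removes children whose gut failure is a passing effect of advanced treatment. Under T2.1, "Participants will be randomised into two groups after completing Phase 1".

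**The concern.** If meeting a single criterion is enough, the *and* before C has no force. If the *and* has force, a single criterion is not enough. Even without the opening sentence, a bare A *or* B *and* C can be grouped in two ways, and they differ over a child with short bowel syndrome who has not had parenteral nutrition for more than 3 months.

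C is the only listed criterion that is not a diagnosis. If it binds only some children, a reader of the trial report cannot tell from the protocol whether all participants had prolonged parenteral nutrition. That would blur which children the quality-of-life result describes. It would also matter for the exploratory question on tolerance of enteral nutrition, which is easier to interpret when participants' dependence on parenteral nutrition is known. Eligibility belongs in the protocol, so a separate analysis plan could not be expected to settle it.

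**Working it through.** There is no planned figure to reproduce; the check is one of logic and context.

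**Step 1. The possible readings.** The inputs are the opening sentence of the Patients paragraph and criteria A, B and C.

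| Reading | Child with A, without C | Does the *and* keep a function? | Does the request for one criterion keep a meaning? |
|---|---|---|---|
| Any one of A, B, C | eligible | no | yes, literally |
| A or (B and C) | eligible | yes | only in part: B alone is not enough |
| (A or B) and C | not eligible | yes | yes, if it refers to the two alternative diagnoses |

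Among the six yes/no combinations that contain A or B, the three readings admit 6, 5 and 3. All of the disputed combinations lack C. These are counts of logical combinations, not of children, and they treat the readings as equally likely. They therefore do not measure the size of the problem.

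**Step 2. Weighing the readings.** The first makes the printed *and* pointless. It would also admit a child on parenteral nutrition alone with neither diagnosis, which is implausible in a trial that identifies its patients through an IF team. The second is grammatically possible, and no other sentence expressly rules it out. The third gives the opening sentence, the *or* and the *and* each a job: the child has one of two qualifying diagnoses, and in either case has had prolonged parenteral nutrition. It is the ordinary way to read such a list.

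Layout adds some caution. Grouping in a short list is often shown by indentation, which can be lost when a PDF is converted to text. The wording of the opening sentence does not depend on layout, but the apparent absence of grouping might.

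**Step 3. Who could be enrolled.** Candidates come from one hospital's IF team, and the title, hypothesis and primary aim all concern children with IF. Both exclusions remove temporary cases. None of this fixes a duration of parenteral nutrition, so it does not prove the third reading. It does mean that a child admitted under the second reading would still be an IF-team patient with short bowel syndrome.

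**Step 4. Consequence for the comparisons.** Whichever reading is used, it is applied before Phase 1, and allocation follows Phase 1. Both arms are drawn from the same enrolled children, so the reading cannot favour one arm. The before-and-after comparison in the intervention group sets each child against itself, so eligibility wording does not distort that either.

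**Step 5. Can a reader still see who was studied?** Intravenous nutrition is recorded before and after Phase 1 and at the end of Phase 2, and diagnosis is taken from the electronic patient record. Past duration of parenteral nutrition is not named as a separate data item. Because it is an entry criterion, however, the recruiting staff have to look it up for each child to whom they apply it.

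**The case for a change.** The strongest case for a change is that the most natural reading is also one that the opening sentence, taken at its word, contradicts. No other sentence confirms it. If follow-up by the IF team already guaranteed more than 3 months of parenteral nutrition, listing C would be redundant; so C restricts someone, and the protocol does not say whom. The exclusions do not help, since lasting short bowel syndrome is not a temporary condition. The repair would be one sentence.

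The textual part of this stands: the two statements do not fit together literally, and A or (B and C) cannot be excluded. What does not stand is the step from loose wording to harm. Inconsistent application is unlikely with one centre, one identifying team and a PhD student or research assistant recruiting. The drift in population is limited to children under the same team's care. No bias arises, and no effect on any result can be shown. That a repair is cheap does not make it necessary.

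**Conclusion.** The concern describes a real looseness in drafting but does not call for a change to the plan. The text leaves one narrow question unstated: whether C also applies to children with short bowel syndrome. The natural reading is that it does. Stating the grouping would put on paper a rule that the investigators can be expected to apply sensibly anyway.

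The effect on the randomised comparison is nil in terms of bias. The effect on the description of the population cannot be quantified, because the protocol gives no number of children with short bowel syndrome and no distribution of time on parenteral nutrition. The conclusion rests on two assumptions: that the IF team applies one rule throughout, and that the report describes participants' diagnoses and parenteral nutrition as reports ordinarily do. If the sponsor amends the protocol for another reason, tidying the sentence would do no harm, but nothing in the design or analysis depends on it.

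### Does the primary aim claim more than a continue-versus-stop comparison can show, and does the control arm rest on an unchecked premise?

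*Protocol*

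**What the plan says.** The primary aim is general: "Determine whether prebiotics improves QoL (primary endpoint) in IF children". It mentions neither earlier exposure nor stopping.

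The design below it is more specific. Under WP1, "The short-time effects of prebiotics on microbiota will be evaluated in an open 4-week intervention", and every participant takes the product in that phase. Under T2.1, "Participants will be randomised into two groups after completing Phase 1": one group carries on with the product, "while the other group will not receive any intervention". T2.2 sets the continued treatment at another six months. The Endpoint paragraph makes the primary comparison QoL between these two groups at that point, scored with two PedsQL questionnaires. No placebo or blinding is named.

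T2.1 gives its reason for the control arm in two consecutive sentences: "Microbiota is known to return to its habitual flora within few weeks after short-term intervention" and "The group without prebiotic treatment will therefore act as a control group".

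On sampling, Task 1.2 states "Data collected at the start of the run-in are: QoL, Stool sample, stool consistency and use of antibiotics". Task 1.3 adds stool before and after Phase 1, and T2.2 adds stool at the end of Phase 2. On comparisons within children, T2.2 says that "the intervention group will serve as their own control before and after the intervention with prebiotics". The Endpoint paragraph also plans within-subject change around prebiotic treatment without limiting it to one arm, and the secondary endpoint covers microbiota change, again without naming an arm.

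**The concern.** Two things draw attention.

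The first is scope. A reader of the aim expects a comparison of children given prebiotics with children not given them. The trial instead randomises only those who got through four open weeks, and compares carrying on with stopping. Children who leave during Phase 1 because of intolerance, dislike or no perceived benefit are outside the comparison. If they would gain less, the effect in all starters is smaller than the effect observed. Families also know whether they still receive sachets, and the outcome is a questionnaire. A conclusion worded like the aim would say more than the data support.

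The second is the premise. The protocol derives the suitability of its control arm from the return of the flora, yet it names the own-control comparison only for the arm that stays on treatment. The stool needed to look at the control arm is apparently already planned, so leaving that comparison unnamed looks like a missed opportunity at little cost.

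**Working it through.** The protocol states no sample size, effect, SD or dropout figure, so there is no figure of its own to reproduce. The inputs below are assumptions, shown over a range.

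**1. Aim against design.** The aim gives the question in one line. T2.1 and the Endpoint paragraph give the population, the arms, the time point and the outcome. They do not conflict: the second set specifies the first more narrowly. No rule or number in the protocol depends on the broader reading.

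**2. How much the scope could matter (illustration).** Let the effect in completers be 0.5 SD, let a share p of Phase 1 starters not be randomised, and let their effect be g. The effect in all starters is (1 − p) × 0.5 + p × g.

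| p | g = 0 | g = 0.25 |
|---|---|---|
| 0.1 | 0.45 | 0.475 |
| 0.2 | 0.40 | 0.45 |
| 0.3 | 0.35 | 0.425 |

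The dilution is modest unless many children are lost. Its one observable input is p, which a participant-flow count supplies. Rewording the aim does not change it.

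**3. What a control-arm stool check could show.** Take an outcome SD of 1, an exchangeable within-child correlation r, and n = 15 or 20 controls (t = 2.145 or 2.093).

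- Against one pre-exposure sample, the variance of the difference is 2(1 − r).
- Against the mean of the run-in and pre-Phase-1 samples, it is 1 + (1 + r)/2 − 2r = 1.5(1 − r).
- The 95% half-width is t × √(variance/n).

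| r | n = 15, one sample | n = 15, two samples | n = 20, one sample | n = 20, two samples |
|---|---|---|---|---|
| 0.3 | 0.655 | 0.567 | 0.554 | 0.480 |
| 0.5 | 0.554 | 0.480 | 0.468 | 0.405 |
| 0.7 | 0.429 | 0.371 | 0.363 | 0.314 |

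An interval this wide could not establish return.

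**4. Whether a departure would mean that the flora failed to return.** Suppose the flora has fully recovered from the prebiotic, but age, diet or antibiotics have moved it by d over the roughly seven months. With two pre-exposure samples and r = 0.5, the noncentrality is d/√(0.75/n).

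| d | n = 15: noncentrality | n = 15: interval excludes zero | n = 20: noncentrality | n = 20: interval excludes zero |
|---|---|---|---|---|
| 0.3 | 1.34 | 24% | 1.55 | 31% |
| 0.5 | 2.24 | 55% | 2.58 | 69% |

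A rule that read such an interval as evidence against the premise would therefore often mislead.

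**5. Timing.** The premise concerns recovery within weeks. The only sample after stopping comes about six months later, so no planned sample tests the premise as stated.

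**6. Dependence of the primary result.** The two arms are formed by randomisation after Phase 1, so both carry the same earlier exposure on average. Incomplete return of the flora would change what stopping means biologically. It would not bias continuing versus stopping.

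**The case for a change.** The strongest argument for a change is that the protocol itself makes the return of the flora the reason for its control arm, then assigns the own-control comparison to the other arm. That is a choice written into the protocol, not a detail it leaves open. Naming the comparison for both arms would use samples already planned and needs no extra patients or visits. One sentence aligning the aim with the contrast would likewise cost almost nothing and would discourage an over-wide conclusion.

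Much of this stands as fact. The aim is broader than the contrast, no blinding is named, and no control-arm comparison after stopping is spelled out. But the text does not shut that comparison out. Control children also took prebiotics in Phase 1, so the planned within-subject changes can include them, and the microbiota endpoint is not confined to one arm. Which within-arm contrasts are estimated is commonly settled in the statistical analysis plan, which is not shown here. The comparison would also be imprecise, come too late to test recovery within weeks, and be open to drift. It concerns flora and not QoL, so it could neither confirm nor undermine the primary result.

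The lack of blinding with a questionnaire outcome is a real limit on interpretation. Adding a word to the aim would not reduce it, and the open design is visible to any reader.

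**Conclusion.** No change to the plan follows. The aim is a short general statement of a question that the design sections then define openly, and the randomised comparison is valid for continuing versus stopping among Phase 1 completers. After six months off the product a large carry-over is unlikely.

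The possible dilution from completers to all starters is 0.025 to 0.15 SD (0.5 − 0.475 to 0.5 − 0.35). This holds only under the assumed 0.5 SD effect, 10% to 30% not randomised, and half or no gain in those children. Reporting handles it: word the conclusion for the contrast and population randomised, and give the number who entered Phase 1 but were not randomised, with reasons.

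Analysts may describe the control children's end-of-study microbiota and short-chain fatty acids against their own pre-Phase-1 samples, provided that controls give stool at that visit, as the between-group comparison implies. Such a description shows the state at six months only and should carry no rule declaring the premise supported or refuted. With both pre-exposure samples, its half-width of 0.31 to 0.57 SD rests on an assumed 15 to 20 controls and correlations of 0.3 to 0.7.

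### The primary endpoint is worded once as the 6-month QoL score and once as changes between the groups; align the two and adjust for the after-Phase-1 score

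*Protocol*

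**What the plan says.** Four consecutive sentences under Endpoint (WP2) matter here. The first defines the endpoint: "Primary endpoint will be QoL score compared between the two groups at 6-months follow-up". The second names two questionnaires. The third gives the schedule: "Scoring will be done at run-in, before and after phase 1 and at the end of phase 2". The fourth draws a consequence from that schedule: "This enables us to study changes between the two groups (primary endpoint) and changes within the subjects before and after intervention with prebiotics".

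The other mentions of the endpoint do not decide between score and change. The primary aim is "Determine whether prebiotics improves QoL (primary endpoint) in IF children", and the Outcomes and measurements table lists "QoL questionnaires: PedsQL and PedsQL Gastrointestinal symptoms scale". Neither gives a time point or a form of the score.

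Two facts about the design bear on the choice of baseline. Everyone takes the product in WP1 (Task 1.3): "Participants are provided with sachets of prebiotics to ingest daily for 4 weeks of Phase 1 intervention". Allocation follows (T2.1): "Participants will be randomised into two groups after completing Phase 1".

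**The concern.** The defining sentence describes a comparison of final values, which needs only the last scoring. The fourth sentence attaches the primary-endpoint label to changes, and it presents those changes as something the repeated scoring makes possible. In the same sentence the same word is used for the within-subject comparison, where it must mean change over time. A reader could therefore take the primary analysis to be a comparison of change scores.

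On that reading the reference scoring is open. Three scorings are scheduled before Phase 2, and they are not interchangeable: two precede any trial prebiotic, and the third follows four weeks of it in all participants.

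At stake is a single definition of the trial's only primary outcome. Two analysts following the protocol could produce different estimates, standard errors and p-values from the same data.

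**Working it through.** **No figure to reproduce.** The protocol as shown states no sample size, SD, correlation, power or effect size. The textual comparison carries the point; the arithmetic shows what depends on the choice.

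**Inputs (all assumed).** Equal variances at both scorings; correlation r between the baseline and end-of-Phase-2 scores of 0.3, 0.5 or 0.7.

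**Step 1: expected difference.** If the baseline is scored before allocation is known, randomisation gives it the same expectation in both arms, so subtracting it leaves the expected between-arm difference unchanged. A simulation with no true effect and a common Phase 1 shift of 0.5 SD in both arms gave mean between-arm estimates within 0.005 SD of zero for score, change and ANCOVA. There is no bias under either reading.

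**Step 2: precision.** Large-sample variance of the treatment effect, with the score comparison set at 1:

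| Comparison | Formula | r = 0.3 | r = 0.5 | r = 0.7 |
|---|---|---|---|---|
| Score | 1 | 1.00 | 1.00 | 1.00 |
| Change | 2(1 − r) | 1.40 | 1.00 | 0.60 |
| ANCOVA | 1 − r² | 0.91 | 0.75 | 0.51 |
| ANCOVA relative to change | (1 − r²) / [2(1 − r)] = (1 + r)/2 | 0.65 | 0.75 | 0.85 |

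Change is less precise than score when r is below 0.5 and more precise when r is above it. ANCOVA is more precise than both at each of these correlations.

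**Step 3: the same ratios as sample size.** For an assumed difference of 0.5 SD, two-sided 5% level, 80% power and 1:1 allocation, n per arm = 2(1.96 + 0.842)² × v / 0.5² ≈ 62.8 × v, where v is the relative variance above. Rounded up:
- score: 63 at every r;
- change: 88 / 63 / 38;
- ANCOVA: 58 / 48 / 33.

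**Step 4: small arms.** With n per arm, the ANCOVA ratio to the score becomes (1 − r²)(1 + 1/(2n − 4)). At an assumed n = 10 the second factor is 1 + 1/16 = 1.0625, so the ratios are 0.91 × 1.0625 = 0.97, 0.75 × 1.0625 = 0.80 and 0.51 × 1.0625 = 0.54. At r = 0.3 almost nothing is gained over the plain score.

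**Step 5: why ANCOVA removes the question.** Write the model as final = a + b·arm + c·baseline + error. Subtracting the baseline from both sides gives change = a + b·arm + (c − 1)·baseline + error. The arm effect b and the residuals are identical, so the standard error and p-value are too. One simulated data set with 15 per arm confirmed this: effect −1.496, standard error 5.040 and p = 0.769 for both outcomes. The identity holds only when the change is taken from the same scoring that serves as covariate.

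**The case against.** The best defence is that the paragraph contains one explicit definition, giving measure, contrast and time, and that the fourth sentence only explains what the schedule allows. What lies between groups is a difference, and the sentence lists within-subject changes as a separate item. T2.2 has the same two parts: it compares the groups and then adds "In addition, the intervention group will serve as their own control before and after the intervention with prebiotics". On that reading nothing conflicts and no baseline is needed. This defence is plausible, and the text does not exclude it. A reader might infer that the protocol flatly contradicts itself; the documents support only an ambiguity.

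Three other stronger inferences also fail:
- *The primary comparison is biased.* It is not (Step 1).
- *The false-positive rate is inflated.* That would require the choice to stay open until the data are seen. The protocol does not say so, and an SAP fixed in advance would prevent it.
- *The missing baseline is itself an omission.* A comparison of final scores needs none, and the details of a change analysis may properly sit in an SAP that is not shown.

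It can also be said that ANCOVA goes further than the wording problem requires. That is fair: rewording one phrase cures the inconsistency. ANCOVA is recommended because it is a better comparison than either stated form and uses data already scheduled.

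**Conclusion.** The point holds as an ambiguity in the definition of the only primary outcome. It should be corrected, with medium confidence, because the innocent reading of the later sentence is a real possibility. An SAP could settle the analysis, but the protocol's two sentences would still need to agree.

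The size is a matter of precision. Over assumed correlations of 0.3 to 0.7, choosing change instead of score moves the variance from 40% higher to 40% lower, and ANCOVA improves on both in large samples. These ratios rest on equal variances and on correlations that the protocol does not give; arm sizes are likewise assumed. The point does not address which of the two questionnaires is primary.

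**What to change.** **Minimum.** Reword the fourth sentence so that its primary-endpoint label matches the defining sentence.

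**Recommended.** In both places, define the primary comparison as the end-of-Phase-2 QoL score between the randomised arms by ANCOVA, with the after-Phase-1 score on the same questionnaire as covariate. A possible later sentence: *The end-of-Phase-2 score will be compared between the randomised groups, adjusted for the after-Phase-1 score (primary endpoint); within-subject changes will be described separately.*

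State also that the after-Phase-1 score is the last before randomisation and is completed before allocation is disclosed. The second condition matters because the control group receives no intervention, so participants will know their arm. Note that this score follows four weeks of open prebiotics in everyone. That does not bias the randomised contrast, but it does affect what a change from this score means.

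**Cost.** One or two sentences of protocol text and one degree of freedom. Both scorings are already scheduled, so no new data are needed. Where the correlation is low and the arms are very small, the gain over the plain score is slight.

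### Does testing the microbiota effect on crude diversity indices throw away each child's own earlier samples?

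*Protocol*

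**What the plan says.** The sentence at issue is in the Protocol, Methods, stool-sample item: "The main effect of the intervention on the microbiota will be tested based on crude alpha and beta diversity indices". It continues "but we will also apply advanced multivariate methods".

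Four other places bear on how those indices will be used:

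- **Secondary endpoint (Endpoint section).** "Secondary endpoint will include changes in the microbiota measured indirectly by the production of SCFAs, the microbiota composition and diversity". The Secondary aims also speak of change, for both the microbiota and the short chain fatty acids.
- **T2.2 Intervention Phase 2, comparisons.** There are two: "We will compare the intervention group with the control group", and in addition "the intervention group will serve as their own control before and after the intervention with prebiotics".
- **T2.2, rationale.** "The study design is useful to account for the inter-individual make-up of the microbiota that contributes to a large portion of variability between subjects".
- **Sampling (Tasks 1.2 and 1.3, T2.2).** Stool is taken at the start of the run-in, before and after the four-week Phase 1, and at the end of Phase 2.

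The protocol gives no variance, within-child correlation, sample size or effect size for any microbiota measure.

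**The concern.** To a statistician, *crude* often means unadjusted. On that reading the main microbiota test would compare the arms at the end of Phase 2 on the raw index values and leave the stable differences between children in the error term. That would sit badly with the rationale in T2.2, which names these differences as a large source of variability and presents the design as a way to handle them. Three of the four stool samples per child would play no part in the test.

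The stake would be power. In a small trial, a real shift within children could be masked by differences between them and reported as no effect, on the endpoint that carries the mechanism in the trial's hypothesis.

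**Working it through.** The protocol states no figure that could be reproduced here. The question is first one of wording, then of what the wording would cost if read the unfavourable way.

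**1. What *crude* is set against.** The sentence has two halves: crude alpha and beta diversity indices on one side, advanced multivariate methods on the other. The contrast is between simple summaries and complex methods. It is not between unadjusted and adjusted, or unpaired and paired, analysis. The sentence names the measure and stops. An arm comparison at the end of Phase 2 that omits earlier samples has to be supplied by the reader.

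**2. Whether these indices rule out pairing.** They do not. Alpha diversity gives one value per sample, so it can be analysed as a within-child change, with baseline adjustment, or in a repeated-measures model. Beta diversity can be analysed as distance from the child's own earlier sample, or with permutations restricted within child. Baseline-adjusted ANCOVA and PERMANOVA on change, the usual remedies, work on the indices the protocol names. Even if *crude* meant unadjusted for covariates, it would not mean unpaired.

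**3. What the surrounding text implies.** An endpoint defined as change needs an earlier value. A group that is its own control needs paired samples. A design said to account for differences between children is evidence of intent to use within-child data. The proof of concept belongs to WP1, which is open and has no control arm. Its comparison can only be before versus after in the same children, and the sentence on diversity indices is not limited to Phase 2.

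**4. What ignoring earlier values would cost (illustration only).** Assumptions: a difference of 0.8 SD, two-sided alpha 0.05, 80% power, 1:1 allocation, and a within-child correlation rho between 0.3 and 0.9. None of these comes from the protocol.

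Per arm, n = 2 × (1.96 + 0.84)² × V / 0.8², rounded up. V is 1 for follow-up values only, 2(1 − rho) for a change score, and 1 − rho² with baseline adjustment. With V = 1 and unrounded normal quantiles this is 24.5, so 25.

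| rho | V, change | n/arm, change | V, adjusted | n/arm, adjusted |
|---|---|---|---|---|
| 0.3 | 1.40 | 35 | 0.91 | 23 |
| 0.5 | 1.00 | 25 | 0.75 | 19 |
| 0.7 | 0.60 | 15 | 0.51 | 13 |
| 0.8 | 0.40 | 10 | 0.36 | 9 |
| 0.9 | 0.20 | 5 | 0.19 | 5 |

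For beta diversity, a PERMANOVA simulation assumed 15 children per arm and 20 features, 4 of them shifted by 0.8 SD, with 200 trials per cell and 199 permutations. Power on end values versus within-child change was:

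- 50% between-child share: 72.5% versus 72%
- 70% share: 67.5% versus 94.5%
- 80% share: 77.5% versus 99%

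The Monte Carlo standard error is about √(0.675 × 0.325 / 200) = 0.033, or 3 percentage points. A separate run with 300 trials per cell gave 73% versus 74%, 73% versus 96% and 70% versus 100%.

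So the cost is large if the correlation is high. At a 50% share, analysing change brings no gain for beta diversity, and for a single index a raw change score only breaks even; baseline adjustment still helps there (V = 0.75). These are general facts about repeated measures. They do not show that this protocol forgoes the gain.

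**The case for a change.** The strongest counter-argument is that the protocol does state a main test and separates it from the additional multivariate work, so the choice is open to criticism as written. An analysis plan drafted from this sentence could inherit *crude* in the sense of unadjusted. Moreover, T2.2 makes only the intervention group its own control. The randomised comparison gets one bare sentence that does not mention earlier values, and an uncontrolled before-after contrast in one arm cannot replace a baseline-adjusted comparison of arms. The samples already exist, and one clarifying phrase would settle the matter.

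Part of this stands. *Crude* is loosely chosen, the own-control sentence does not by itself shape the randomised comparison, and a clarification would be cheap. But the endpoint, defined as change, is not confined to one arm, and silence about a model is not a decision to leave out earlier values. What remains is an unnamed model and time contrast for a secondary endpoint. Protocols commonly leave that to the statistical analysis plan, and its absence here cannot be counted as an error.

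**Conclusion.** The concern does not hold. The protocol names simple diversity indices as the main microbiota measure. It does not commit to an unpaired or unadjusted test, and its endpoint definition, own-control comparison and design rationale all point towards using each child's earlier samples. Its remark that differences between children make up "the inter-individual make-up of the microbiota that contributes to a large portion of variability between subjects" supports that intent. It gives no number and does not say that such differences dominate.

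No loss can be attributed to the plan. The illustrative figures, such as 25 versus 13 children per arm at a correlation of 0.7, rest wholly on an assumed correlation, effect and design, and would apply only if the analysis in fact ignored earlier values. This conclusion rests on the protocol alone. A statistical analysis plan that specified an end-of-Phase-2 comparison without earlier values would reopen the question.
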